9.2.3. Blind maintenance

In the process of the blinding, the staffs responsible for preparing the vaccine are non-blind person, who know distribution of participants because the vaccine group A (high dose group) and vaccine group B (low dose group) need different vaccine preparation methods (see 9.3.2).

Besides the staffs for vaccine preparation, all other researchers do not know the treatment allocation of participants. The two un-blinded staffs only responsible for the vaccine preparation, are not allowed to do any records or tell any person the distribution of participants or participate in the test of any other work (including follow-up observations).

After the visit of 28 days after vaccination, the data will be checked by the statistical part and then locked for the interim analysis. The data will be unblinded. Serious adverse event after day 28 and final visit at month 6 will be opened. But the staffs responsible for the laboratory tests will be kept in blinded during the whole study, including the serum tests at month 6.

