7.2.2. Secondary endpoints

7.2.2.1. Safety

- Occurrence of unsolicited adverse reactions within 28 days after vaccination.
- Occurrence of serious adverse reaction during the whole follow-up period (6 months).
- Post-vaccination Rate of infected with HIV.

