9.2. Randomization and Blinding

9.2.1. Randomization and blinding method

Randomization list will be generated by independent statistician using SAS software. The independent statistician will generate the randomization list of 500 random codes, randomly allocated these codes to the high dose vaccine, or low dose vaccine, or placebo in a ratio of 2:1:1, using a “Proc plan” procedure in SAS by block randomization. Each person dose of investigational vaccines is assigned

a code from a randomization list. The package of the investigational vaccine (including high dose vaccine, low dose vaccine and placebo) will be relabeled, using identical package with a randomized code which is the unique identifier for each person dose. Therefore, all the vaccine and placebo doses are blindly coded. The persons who participate in randomization and blinding must not participate in any other process of the clinical trial, also must not disclose the contents of blinding to any personnel. Eligible participants enrolled into this study, will be assigned a sequential number according to their sequence of enrolment and received vaccine or placebo labelled with the same numbers. Thus, participants are randomly assigned to receive high dose vaccine, or low dose vaccine, or placebo in a ratio of 2:1:1.

The independent statistician should produce a copy of emergency blinding code which should note the title of program and the character “To Be Opened Only in Case of Emergency”. Personnel who involved in randomization and blinding are not allowed to participate in any other procedure in this study.

Blinding will be maintained for all participants and investigators and their study staff participating in this study.

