9.2.2. Method of blind breaking and unblinding

When the last participant completed the 28 day visit, CRF completion, a database entry and blind state audit should be completed. Un-blinding should be after the publication database lock statement when all parties involved in such as the sponsor, investigator, statistical representatives.

During the study, the breaking of the treatment code is forbidden, except in the event of a medical emergency when the investigator believes it is necessary to determine the treatment code in order to initiate appropriate treatment. If knowledge of the treatment code is required, the investigator will open only the specific participant’s code envelope. A signature, date, time and reason will be written on the opened code envelope and the participant with this code has to be withdrawn from this study.

The investigator will assess the relationship between the adverse event and the investigational products before the treatment code is un-blinded. The investigator will immediately notify the sponsors at the 24 hours emergency call number ([name] [name]) when the treatment code blinding is broken on any participant for any reason during the study. The reason for the blinding being broken

must also be documented in the participant's medical records and in the CRF.

At the end of the study, all code envelopes (intact and opened) must be accounted for and are to be collected by the monitor to be destroyed.

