9.7.2. Interim analysis

After the last participant complete the Visit 3 (28 days after vaccination), the data of the clinical trials from Visit 1 to Visit 3, will be entered into the database for blind review. Then database (Visit 1 to 3) is locked, interim analysis will be done by the independent statistical party. Statistical party must not divulge blinded code. The clinical trial sites still remain in blinded.

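### Sections 9.2.3 and 9.7.2 give opposite rules on blinding after the day-28 lock, which leaves the six-month secondary safety endpoints open to bias if 9.2.3 is followed

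*Protocol*

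**What the plan says.** Four parts of the Protocol deal with the blind after the day-28 visit.

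- **9.2.3 Blind maintenance.** After the day-28 visit the data are checked and locked for the interim analysis. Then: "The data will be unblinded". And: "Serious adverse event after day 28 and final visit at month 6 will be opened". One group is exempted: "But the staffs responsible for the laboratory tests will be kept in blinded during the whole study, including the serum tests at month 6".
- **9.2.2 Method of blind breaking and unblinding.** The opening paragraph ties unblinding to the lock that follows the last participant's day-28 visit, and names sponsor, investigator and statistical representatives as parties to it. The next paragraph forbids breaking the code during the study except in a medical emergency.
- **9.7.2 Interim analysis.** On the same lock: "Statistical party must not divulge blinded code". And: "The clinical trial sites still remain in blinded".
- **9.2.1 Randomization and blinding method.** "Blinding will be maintained for all participants and investigators and their study staff participating in this study". No end date is given.

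The outcomes that run past day 28 are the secondary safety endpoints of 7.2.2.1 (serious adverse reactions over six months, and HIV infection after vaccination) and the month-6 antibody measurements.

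**The concern.** A site that follows 9.2.3 works with known allocation after the interim lock. A site that follows 9.7.2 does not. The choice matters because the later safety data depend on reporting and judgement:

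- Section 9.4.1 ends active collection of adverse events at day 8. SAEs are still recorded at visits (Table 7-3-2), but no visit falls between day 28 and day 168, so capture in that stretch leans on what participants report and how staff respond.
- Relatedness is a yes/no judgement by the investigator (9.4.4), and the endpoint in 7.2.2.1 is worded as a reaction.
- New HIV diagnoses between visits reach the site by self-report (9.4.6), and 9.5.3.2 compares HIV incidence between vaccine and placebo. Section 12.3.1 itself says the vector may raise HIV risk, so staff who know the arm have a reason to ask, counsel or follow up differently.

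Under 9.2.3 as written, randomisation would no longer be backed by blinding for these comparisons.

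**Working it through.** **1. The rules side by side**

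| Question after the day-28 lock | 9.2.3 | 9.2.2 | 9.7.2 | 9.2.1 |
|---|---|---|---|---|
| Is the code released? | Data unblinded; recipients not named | Opening paragraph: yes, at this lock. Next paragraph: no code breaking during the study except in an emergency | Must not be divulged | Not addressed |
| Are site staff blinded? | Only laboratory staff are said to stay blinded | Investigator named as a party to the unblinding | Yes | Yes, no end date |

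For SAEs after day 28 and for the month-6 visit, no conduct satisfies every cell. Section 9.2.2 also disagrees with itself.

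Three other places assume a blind that lasts beyond the interim. Section 9.4.5 allows investigators to unblind single cases only where participant safety requires it. Section 9.7.6 has the DSMB unblind reported cases if HIV incidence crosses a threshold, although the only scheduled HIV test after baseline is on day 168 (9.5.3.1). Section 9.7.3 calls for blind review before the final lock.

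**2. How much follow-up could be open**

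The Protocol states no figure, so there is none to reproduce.

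Inputs:
- Follow-up ends on day 168 and the last pre-interim visit is day 28 (Table 7-3-1).
- The lock waits for the last participant's day-28 visit (9.2.2, 9.7.2).
- *w* = days from a participant's own day 28 to the last participant's day 28.
- *E* = length of enrolment. The timetable in section 11 has an ambiguous one-month row marked for reference only, so *E* = 30 days is an assumption. Enrolment is taken as uniform, so mean *w* = *E*/2.
- *L* = lag from the last day-28 visit to the lock. The Protocol gives none, so a range is shown.

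Open share = (168 − 28 − *w* − *L*) / 168.

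| Case | Calculation | Share |
|---|---|---|
| Last participant, *L* = 0 (maximum) | 140/168 | 83.3% |
| First participant, *E* = 30, *L* = 0 | (140 − 30)/168 = 110/168 | 65.5% |
| Mean, *E* = 30, *L* = 0 | (140 − 15)/168 = 125/168 | 74.4% |
| Mean, *E* = 30, *L* = 14 | (125 − 14)/168 = 111/168 | 66.1% |
| Mean, *E* = 30, *L* = 30 | (125 − 30)/168 = 95/168 | 56.5% |
| Mean, *E* = 30, *L* = 60 | (125 − 60)/168 = 65/168 | 38.7% |
| Mean, *E* = 60, *L* = 0 | (140 − 30)/168 = 110/168 | 65.5% |
| 9.7.2 governs | – | 0% |

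The visit windows (±3 and ±10 days) move the maximum between (158 − 31)/158 = 80.4% and (178 − 25)/178 = 86.0%.

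This is a share of time, not of events. For HIV it is a poor measure, because the single scheduled post-baseline test falls at the very end of follow-up.

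**The case against.** The best defence is that a staged design was intended: blind to day 28, then open. The opening paragraph of 9.2.2 agrees with 9.2.3, the primary safety endpoint (solicited reactions to day 7) is complete before any opening, the ELISA is read by blinded staff throughout, and the safety analysis is mainly descriptive (9.7.5.1). This stands as far as it limits the damage to secondary endpoints. It does not remove the conflict, because 9.7.2 is just as explicit in the other direction.

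Several stronger readings are tempting, and the documents do not support them:

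- **That 83% is the expected open share.** It is a maximum, as shown above.
- **That participants are told their arm.** No section says so, and 9.2.1 says the opposite. Section 9.2.3 does not name who receives the code. Opening to site staff is the natural reading, since only the laboratory is exempted, but it is still a reading.
- **That HIV tests are read with the arm known.** HIV detection sits in the laboratory section (9.5), so the laboratory exception may cover it. The test uses finger blood and the reader is not named, which calls for clarification only.
- **That open relatedness judgements would drive the pause rule in 7.5.** That rule halts injections and enrolment. In a single-dose trial both are finished once the last participant has passed day 28. The DSMB also determines relatedness (9.7.6) and takes the final decision (7.5).
- **That only related SAEs are compared.** Section 9.4.2.2 already describes all SAEs by group.
- **That causality must always be judged before unblinding.** The sentence "The investigator will assess the relationship between the adverse event and the investigational products before the treatment code is un-blinded" follows the emergency code-break procedure and reads as part of it, so it is weak evidence for a general rule.

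**Conclusion.** The contradiction is real and in the current text: 9.2.3 and the opening of 9.2.2 against 9.7.2, 9.2.1 and the rest of 9.2.2. If 9.2.3 governs, and if opening includes site staff, up to 83% of follow-up could be conducted with the arm known. The mean is about 74% under one month of uniform enrolment and an immediate lock, and lower with any lag. If 9.7.2 governs, nothing is exposed.

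What is at risk is the ascertainment and relatedness of SAEs after the lock, and HIV diagnoses reported between visits. The direction and size of any bias cannot be calculated from the Protocol. The point should be settled before the interim lock, because unblinding cannot be reversed.

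**What to change.** Bring 9.2.2 and 9.2.3 into line with 9.7.2 and 9.2.1:

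- After the day-28 lock, individual codes are held only by the independent statistical party, and by the DSMB where it needs them.
- Only group-level day-28 results are released. Individual antibody results should be held back too: 9.7.1 assumes 85% and 95% positive in the vaccine arms against no more than 5% on placebo, so a single result would often reveal vaccine or placebo.
- Participants, site staff, those who assess SAEs and whoever reads the HIV test stay blinded until the day-168 lock. Name the HIV test reader.
- Delete or reword the sentences in 9.2.3 that unblind the data and open later follow-up. Limit the opening paragraph of 9.2.2 to the statistical party at the interim, with full unblinding at the final lock.

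The cost is that individual allocations are released about five months later (140 days from the last participant's day 28 to day 168) and that the blind must be kept up at the site for that time. The interim analysis can still be run and reported on schedule.

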9.3. Vaccine inoculation

9.3.1. Experimental vaccine Ad5-EBOV

Experimental vaccine Ad5-EBOV, developed by Beijing Institute of Biotechnology and Tianjin CanSino Biotechnology Inc., is a replication defective Adenovirus Type 5 Vector based vaccine which expresses Ebola virus Zaire (Guinea, 2014) envelope glycoprotein. The final product is lyophilized white powder, with 4.0×10^{10} vp/vial. The antigen contents in the Ad5-EBOV were measured according to Ebola vaccine antigen standard by the National Institute for Food and Drug Control (NIFDC).

The placebo is lyophilized-dried powder, contains same formulation of excipients as vaccine, with no virus particle which could express Ebola virus Zaire envelope glycoprotein. The placebo was also measured to be qualified by NIFDC.

The sterile water for injection is developed by SINOPHARM GROUP CO. LTD. (Lot: 1405544-All), 2ml per vial. The expire date is 2017, 04,

9.3.2. Administration

One injection will be allocated intramuscularly in the arm at day 0.

Experimental vaccine group A (4×10^{10} vp/vial, 4 vials): 1 ml sterilization injection water per dose to dilute 2 vials (4×10^{10} vp/vial), one shot in each arm, total dose of 1.6×10^{11} vp. The inoculation site was the central lateral deltoid in the upper arm, and inoculation route was intramuscular injection

Experimental vaccine group B (4×10^{10} vp/vial, 2 vials): 1 ml sterilization injection water per dose to dilute 1 vial (4×10^{10} vp/vial), total dose of 8×10^{10} vp, one shot in each arm. The inoculation site was the central lateral deltoid in the upper arm, and inoculation route was intramuscular injection

Placebo group (0 vp/ vial, 2 vials): 1 ml sterilization injection water per dose to dilute 1 vial, total dose of 0 vp. The inoculation site was the central lateral deltoid in the upper arm, and inoculation route was intramuscular injection

Before injection, 75% alcohol is used for disinfection at the injection site and intramuscular vaccination will be administrated several minutes later. Shaking the vaccine before use and make vaccine fully dissolved in sterile water for injection. No intravascular, intradermal or subcutaneous injection is allowed with the investigational vaccine. During the vaccination and 60-minute safety surveillance after vaccination, appropriate emergency medical equipment and doctors should put on standby in case that possible allergic reaction after injection.

Only the qualified doctors, Community Health Officer (CHO) or qualified nurse will give the injection. For the purpose of vaccine/placebo administration, a medically qualified member of the study staff is a study physician or a study nurse, as applicable to the investigator's local practice.

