Clinical Director [name] [name] Connaught Hospital, Freetown, Ministry of Health & Sanitation, Sierra Leone

This document contains confidential information belonging to
Beijing Institute of Biotechnology and Tianjin CanSino Biotechnology Inc.
All rights reserved and all materials not authorized may not be copied or used

PROTOCOL SUMMARY

Brief Title	A Phase II Clinical Trial to Evaluate the Recombinant Human Type 5 Adenovirus Vector Based Ebola Virus Disease Vaccine (Ad5-EBOV) in Healthy Adults
Official Title	A Single-Center, Randomized, Blind, Phase II Clinical Trial to Evaluate the Safety and Immunogenicity of the Adenovirus Type 5 Vector Based Ebola Virus Disease Vaccine (Ad5-EBOV) in Healthy Adults Aged Between 18 and 50 years in Sierra Leone
Objectives	Preliminarily evaluate the safety, immunogenicity of the Adenovirus Type 5 Vector Based Ebola Virus Disease Vaccine (Ad5-EBOV) after one injection under dosage of 8×10^{10} vp or 1.6×10^{11} vp; to determine appropriate dosage which could support large-scale phase III clinical trials
Target disease	To prevent Ebola virus disease caused by Zaire type Ebola virus infection
Target population	Healthy adults age between 18 and 50 years in Sierra Leone
Sample size	500 participants
Rational and background	
Ebola viruses (EBOVs) are known to cause fatal hemorrhagic fever in humans and non-human primates with a mortality rate up to 90%. EBOV is transmitted among humans through close contact with the infected blood, bodily fluids or tissues; also, the intentional release of EBOVs would probably result in mucosal infection by small-particle aerosol dispersion.
 
Five different species of EBOV have been identified: Zaire, Sudan, Ivory Coast, Reston and the newly discovered Bundibugyo. Among these species, infection with Zaire is the most serious and has caused the greatest number of deaths.
 
The EBOV envelope glycoprotein (EBOV-GP) forms spikes on the surface of mature virions, and has been shown to be an effective target for vaccine design. Preclinical studies indicated that both humoral and cellular responses to EBOV

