	
Affiliated Hospital of Medical College of Zhejiang University, started from Apr 3, 2015 (ClinicalTrials.gov, number NCT 02401373). Two dose groups were set, and the number of participants in the lower dose group (8×10^{10} vp) and the higher dose group (1.6×10^{11} vp) was 31 and 30, total 61 participants in two groups. There was no serious adverse reaction in all the participants. Ebola glycoprotein-specific antibody titers were significantly increased in participants in the low-dose and high-dose vaccine groups at both day 14 (geometric mean titer 1370.9 and 1185.5, respectively) and day 28 (1918.7 and 1684.7, respectively). T-cell responses also peaked at day 14.

Investigational vaccines	
Recombinant human type 5 adenovirus vector based Ebola vaccine was jointly developed by Beijing Institute of Biotechnology and Tianjin CanSino Biotechnology Inc.
 
Experimental Vaccine: lyophilized white powder, with recombinant replication defective human recombinant Ad5 vector based vaccine expressing Ebola virus glycoprotein 4×10^{10} vp/ vial. The quality was conformed to the requirements of manufacturing and verification of the recombinant Ebola virus disease vaccine formulated by the sponsors and tested and certified by National Institute for Food and Drug Control (NIFDC), Chinese Food and Drug Administration.
 
Placebo Control: lyophilized white powder, other components were consistent with the experimental vaccine excluded recombinant replication defective human recombinant Ad5 vector based vaccine expressing Ebola virus glycoprotein, tested and certified by National Institute for Food and Drug Control (NIFDC).
 
Immunization schedule: Experimental vaccine group A: one-time inoculation; 1 ml sterilization injection water per dose to dilute 2 vials (4×10^{10} vp/vial), total dose of 1.6×10^{11} vp, one shot in each arm. Experimental vaccine group B: one-time inoculation; 1 ml sterilization injection water per dose to dilute 1 vial (4×10^{10} vp/vial), total dose of 8×10^{10} vp, one shot

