	
in each arm.
 
Placebo group: one-time inoculation; 1 ml sterilization injection water per dose to dilute 1 vial (0 vp/vial), total dose of 0 vp, one shot in each arm.
 
Inoculation site and inoculation route:
 
The inoculation site was the central lateral deltoid in the upper arm, and inoculation route was intramuscular injection
 
Storage and transport conditions:
 
To store and transport in 2-8 °C, avoid light.

Trial design	
Experimental design:
 
This is a single center, randomized, blind, placebo controlled, phase II clinical trial.
 
Clinical Trial Site:
 
Sierra Leone-China Friendship Hospital in Freetown, Sierra Leone
 
Sample size calculation:
 
According to the results of Phase I clinical trial in Jiangsu, we assume that the positive rate of low-dose and high-dose vaccine groups was 95% and 99.9% respectively and placebo only 5%, the ratio will be set as (high-dose: low-dose: placebo)=2:1:1 in order to assure 80% of certainty when the α value is 0.05. Over 207 people in high-dose vaccine group are needed and 104 people in low-dose and in placebo group respectively. A 15% visit loss rate was assumed so we set the sample size as 250 people in high-dose vaccine group, 125 people in low-dose and placebo group, respectively. The total sample size is 500 people.
 
Randomization and blind operation:
 
Randomization list will be generated by an independent statistician using SAS version 9.1 software or a higher version. In this study, all the participants will be recruited and randomly assigned to receive the Ad5-EBOV as (high-dose: low-dose: placebo) =2:1:1. Blinding will be maintained for all participants, investigators and study staff participating in this study.
 
Research plan:

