5.9. Package

The vaccine will be packed in a box with labels. The label contains at least the following information: vaccine name, lot number and duration of vaccine, and vaccine preservation conditions and “only for clinical studies”. Sample of label on the vial:

Only for clinical studies
 
Recombinant Human Type 5 Adenovirus Vector
 
Based Ebola Virus Disease Vaccine
 
4×10^{10} vp/vial
 
Lot: 201501002
 
Date: 2015.01.28
 
Exp: 2016.01.28
 
Storage: at 2~8°C, avoid light
 
Beijing Institute of Biotechnology
 
Tianjin CanSino Biotechnology Inc.

Sample of label on the packaging box:

Only for clinical studies
 
Recombinant Human Type 5 Adenovirus Vector
 
Based Ebola Virus Disease Vaccine
 
For one individual
 
Lot: 201501002

Date: 2015.01.28 Exp: 2016.01.28

Storage: light avoided 2~8°C

- Usage and dosage: add 1ml water for injection solution, use immediately after shaking, intra-muscular injection at the lower edge of deltoid muscle in upper arm of 0.5ml.

Contraindications:(1) Allergic to any ingredient of the Ad5-EBOV (2) Acute disease, severe chronic diseases, chronic disease acute exacerbation and fever (3) Seizure, epilepsy, brain or other mental disease(4)Adults over the age of 18, excluding pregnant women.

Adverse reactions:

Notice:

(1) Cracked vials, unclear or failure label, abnormal appearance after rehydration are not allowed to use; (2) Drug as adrenaline should be equipped for use in case of severe allergic reaction. The participants should be observed at least 60 minutes after injection.

Producers: Beijing Institute of Biotechnology/Tianjin CanSino
Biotechnology Inc.

Address: [name] / [name]
[name]

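### Section 9.3.2 opens with a single injection but then requires one shot per arm, and the 5.9 sample label gives half the volume per shot that the stated doses need

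*Protocol*

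**What the plan says.** The opening sentence of Protocol 9.3.2 reads "One injection will be allocated intramuscularly in the arm at day 0". The paragraphs for groups A and B in the same section then call for "one shot in each arm". Group A has 4 vials per person, 2 of them dissolved in each 1 ml, for a total of 1.6×10^11 vp. Group B has 2 vials per person, 1 in each 1 ml, for a total of 8×10^10 vp. Each vial holds 4×10^10 vp (9.3.1).

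The placebo paragraph of 9.3.2 reads "Placebo group (0 vp/ vial, 2 vials): 1 ml sterilization injection water per dose to dilute 1 vial, total dose of 0 vp" and does not say how many shots are given. The immunization schedule in the protocol summary does: "total dose of 0 vp, one shot in each arm".

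The summary also uses looser terms for the whole vaccination. Its objectives speak of the vaccine "after one injection under dosage of" the full dose, and its schedule has "Experimental vaccine group A: one-time inoculation".

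Section 5.9 prints a usage text under "Sample of label on the packaging box": "add 1ml water for injection solution, use immediately after shaking, intra-muscular injection at the lower edge of deltoid muscle in upper arm of 0.5ml". Section 9.3.2 places the injection at the central lateral deltoid. It gives the diluent volume for each dose but never states the volume to inject.

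**The concern.** The section that tells staff how to give the vaccine states the number of injections in two incompatible ways. The only injected volume for participants in the text at hand is the label's 0.5 ml, taken from a 1 ml reconstitution. Either statement, followed as written, leads to a dose below the assigned one.

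The trial's purpose is to choose between 8×10^10 and 1.6×10^11 vp for phase III (Sections 1 and 6). If both groups received half, the ratio between them would stay at 2:1, but the results would be credited to doses that nobody received. The immunogenicity and solicited-reaction endpoints would both be affected.

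**Working it through.** **Inputs.** Vial content 4×10^10 vp (9.3.1). Vials per person: A 4, B 2, placebo 2 (9.3.2). Vials per 1 ml: A 2, B 1, placebo 1 (9.3.2). Stated totals: A 1.6×10^11 vp, B 8×10^10 vp (9.3.2 and summary). Label volume 0.5 ml (5.9).

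**Formula.** Total dose = shots × ml per shot × vials per ml × 4×10^10 vp.

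**Step 1: reproduce the stated doses.** With two shots of 1 ml:
- A: 2 × 1 × 2 × 4×10^10 = 1.6×10^11 vp.
- B: 2 × 1 × 1 × 4×10^10 = 8×10^10 vp.

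Both match exactly. They also equal vials per person times vial content (4 × 4×10^10 and 2 × 4×10^10). With two shots, the volume needed per shot is 1.6×10^11 / (8×10^10 per ml) / 2 = 1 ml in A and 8×10^10 / (4×10^10 per ml) / 2 = 1 ml in B. For placebo, 2 vials at 1 vial per dose gives two shots, as in group B.

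**Step 2: apply the two conflicting statements.**

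| Reading | A (vp) | B (vp) | Share of stated dose |
|---|---|---|---|
| Two shots of 1 ml | 1.6×10^11 | 8×10^10 | 100% |
| One shot of 1 ml (opening line taken literally) | 8×10^10 | 4×10^10 | 50% |
| Two shots of 0.5 ml (label volume, both arms) | 8×10^10 | 4×10^10 | 50% |
| One shot of 0.5 ml (both taken literally) | 4×10^10 | 2×10^10 | 25% |

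In either 50% row, group A receives the dose assigned to B, and B receives 4×10^10 vp, which is not a dose under study here.

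**Step 3: would vial accountability reveal it?** The 500 planned participants need 250×4 + 125×2 + 125×2 = 1,500 vials, not counting the spares in 9.3.4. With one 1 ml shot for everyone, half would stay unopened: 250×2 + 125×1 + 125×1 = 750. Reconciliation under 9.3.3 and 10.2 would show that. With 0.5 ml in each arm, every vial is opened and 1 of the 2 ml prepared per person is not injected, so a count of vials alone would not show it. Section 10.2 also asks for remaining quantities; whether that covers leftover volume is not stated.

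**The case against.** The strongest reply is that the regimen is never really in doubt. The summary gives one shot per arm for all three groups, 9.3.2 repeats it for A and B, and the vial counts and totals fit nothing else. The opening line most likely means one vaccination occasion, since the summary's objectives use the same singular for the whole dose. The label is a sample in the product background section. It states no number of injections and does not mention group A's two vials per 1 ml. Section 9.2.1 plans to relabel every pack, and 9.2.3 sends the preparers to 9.3.2. Site procedures in the appendices are not at hand and may be explicit.

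Most of this stands, and it is why the risk is modest. It does not remove the contradictions. Section 9.3.2, the text relied on to override the label, is itself inconsistent and gives no injected volume. Section 9.2.1 specifies identical packaging and a random code but does not say that the usage text will change.

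A reader might go further and infer that placebo recipients get one injection and vaccine recipients two, which would unblind participants and injectors and give placebo fewer sites for local reactions. The documents do not support that. The opening line is not limited to placebo: read literally, it gives every group one injection. The unequal reading applies it to placebo alone, overrides it for A and B, and ignores both the second placebo vial and the summary. It is a possible misreading of an incomplete paragraph, not something that the protocol prescribes.

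**Conclusion.** Two errors in current text hold: the singular opening line of 9.3.2, and the 0.5 ml volume on the 5.9 sample label, whose lower-edge deltoid site also differs from 9.3.2. Each, followed literally, delivers 50% of the stated dose in both vaccine groups; for the label this assumes a shot in both arms. The missing phrase in the placebo paragraph is an omission that should be filled.

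The planned doses themselves are right, and the intended regimen (two full 1 ml shots, one per arm, in all groups) can be recovered. It would therefore be wrong to conclude that the doses are undefined or that participants will be underdosed. This should be fixed because it concerns dosing instructions in a dose-selection trial. It does not undermine the design, and the sample size is not involved.

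**What to change.** - **9.3.2, opening sentence.** Replace with: *One vaccination at day 0, given as two 1 ml intramuscular injections, one in the central lateral deltoid of each arm, in all three groups.* This also supplies the missing injected volume.
- **9.3.2, placebo paragraph.** Add "one shot in each arm", as for groups A and B and as in the summary.
- **5.9, label.** Change the usage text to the full 1 ml per injection at the central lateral deltoid, and carry it onto the packs at the relabelling already planned in 9.2.1.

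The cost is two wording changes in 9.3.2 and one label correction. Vaccine supply, sample size and visits are unchanged.
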